4.11.3. Narratives

The following are “notable” events, from start of study intervention through end of study participation (or data cutoff for the submission if earlier):

- deaths
- SAEs
- Severe AESI (referred to [6.1](#) [Appendix 1])

- pregnancy, and
- permanent discontinuations of study intervention due to AEs.

Narratives (patient-level data and summary paragraph) will be provided for participants in the mITT population with at least 1 notable event.

Safety topics of interest are not considered notable events, unless 1 of the above criteria is met. Displays with individual participant-level data will be created for safety topics of interest using various formats such as a customized listing and/or a customized graphical patient profile as specified in the section associated with the safety topic of interest. Medical case summaries or vignettes will be provided if deemed relevant for the discussion of the safety topic of interest.

4.11.4. Additional Safety Assessments

4.11.4.1. Hypoglycemic Events

Definitions of different categories of hypoglycemic events are included in [Table GPIU.4.3](#).

Table GPIU.4.3. Definitions of Hypoglycemic Event Categories

Glycemic Criteria/Description	
Level 1 (Glucose Alert Value)	Blood Glucose <70 mg/dL (3.9 mmol/L) and \geq 54 mg/dL (3.0 mmol/L)
Level 2 (Clinically Significant Hypoglycemia)	Glucose <54 mg/dL (3.0 mmol/L)
Level 3 (Severe Hypoglycemia)	A severe event characterized by altered mental and/or physical status requiring assistance for recovery (no specific glucose threshold).

Nocturnal hypoglycemia: a hypoglycemia event (including severe hypoglycemia) that occurs between bedtime and waking.

Severe hypoglycemia: Defined as an episode with severe cognitive impairment requiring the assistance of another person to actively administer carbohydrate, glucagon, or other resuscitative actions. Severe hypoglycemia will be reported as an SAE. Severe hypoglycemia will be considered as adverse event of special interest (AESI).

To avoid duplicate reporting, all consecutive blood glucose (BG) values <70 mg/dL (3.9 mmol/L) occurring within a 1-hour period may be considered to be a single hypoglycemic event.

Summaries and analyses will exclude hypoglycemic events occurring after initiation of a new antihyperglycemic therapy. For severe hypoglycemia and level 2 hypoglycemia, incidence as well as rate per patient year of exposure will be provided by treatment at specified time intervals. A listing of hypoglycemic events will also be provided. Safety analyses might be conducted after including data after the introduction of another antihyperglycemic therapy.

The incidence of hypoglycemic event will be analyzed using logistic regression with treatment and stratification factors as fixed effects. The rate of hypoglycemic episodes per patient year may be analyzed using a generalized linear mixed-effects model assuming the number of hypoglycemic episodes follows a negative binomial distribution with the mean modeled using stratification factors and treatment as fixed effects. When the number of hypoglycemic events is less 10, a listing of hypoglycemic events will be provided instead.

4.11.4.2. Severe Persistent Hyperglycemia

A summary of initiation of rescue therapy in response to severe, persistent hyperglycemia will be provided by treatment. If there are sufficient number of episodes (≥ 10), time-to-first-event analyses for the initiation of rescue therapy will be conducted by treatment using a cox proportional regression model. For patients without event “time-to-event”, event time will be censored at end of treatment period. A listing of patients who initiated rescue therapy will be provided.

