2.3.3. Overall Benefit Risk Conclusion

The safety and efficacy profile seen to date for tirzepatide, supports the overall benefit risk for participants in this study. Considering the measures taken to minimize risk to participants in this study as outline in the protocol, the potential risks identified in association with tirzepatide are justified by the anticipated benefits that may be afforded to participants living with T2DM.

3. Objectives, Endpoints, and Estimands

| Objectives | Endpoints |
|---|---|
| Primary | |
| 
 To demonstrate that tirzepatide QW 5 mg, and/or 10 mg, and/or 15 mg are superior to placebo QW in HbA1c change from baseline to Week 40 | 
 Change in HbA1c from baseline |
| Key Secondary (controlled for type 1 error) | 
 Proportion of participants with HbA1c target values of <7.0% (<53 mmol/mol) Change in fasting serum glucose (central laboratory) from baseline Proportion of participants with HbA1c target values of ≤6.5% (≤48 mmol/mol) Change in body weight from baseline Proportion of participants with HbA1c target values of <5.7% (<39 mmol/mol) |
| Additional Secondary (not controlled for type 1 error) | 
 Change in daily average 7-point self-monitored blood glucose profiles from baseline Proportion of participants who achieved weight loss of ≥5%, ≥10%, and ≥15% |
| Safety | 
 Incidence of treatment-emergent adverse events Incidence of early discontinuation of study intervention due to AEs Incidence of adjudicated pancreatic AEs Change in serum calcitonin from baseline Incidence of allergic and hypersensitivity reactions Change in systolic blood pressure, diastolic blood pressure and pulse rate from baseline Occurrence of hypoglycemic episodes Time to initiation of rescue therapy for severe persistent hyperglycemia |

CCI

Abbreviations: AE = adverse events; HbA1c = hemoglobin A1c; CCI

QW = once weekly; CCI

Primary estimand

The primary efficacy assessment is guided by the “treatment-regimen” estimand. This estimand aims at reflecting how participants with T2DM are treated in clinical practice and takes into account both tolerability and efficacy.

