4.1. Overall Design

Study GPIU is a multicenter, randomized, double-blind, parallel, placebo-controlled, Phase 3 study which will investigate the efficacy and safety of tirzepatide monotherapy compared with placebo in Chinese participants with T2DM, inadequately controlled with diet and exercise alone, and have not been treated with any antihyperglycemic medication during the 90 days preceding the start of the study.

Approximately, 200 participants will be randomized in a **CCI** ratio (tirzepatide 5 mg QW, 10 mg QW, 15 mg QW, and placebo QW). Participants will be stratified based on HbA1c [$\leq 8.5\%$ (≤ 69 mmol/mol) or $> 8.5\%$ (> 69 mmol/mol)], and any past prior use (Yes or No) of any antihyperglycemic medication.

Study GPIU will consist of 3 periods:

- Period I: approximately **CCI** screening/lead-in period
- Period II: **CCI** treatment period, and
- Period III: **CCI** safety follow-up period.

Study Period I (Screening and Lead-in)

Screening (Visit 1)

The purpose of screening procedures at Visit 1 is to establish initial eligibility and to obtain blood samples for laboratory assessments needed to confirm eligibility at Visit 2. The participant will sign the informed consent form (ICF) before any study procedures are performed. Procedures at this visit will be performed as shown in the SoA (Section 1.3).

Lead-in (Visit 2 to Visit 3)

At Visit 2, the screening laboratory results will be reviewed. For those participants meeting all other eligibility requirements, a dilated fundoscopic examination, performed by an ophthalmologist or optometrist, will be completed between Visit 2 and Visit 3 to confirm eligibility unless a dilated fundoscopic examination was performed by an ophthalmologist or optometrist within 90 days of study entry (Visit 1) (section 5.2 Exclusion Criterion [10]).

Additionally, at Visit 2, participants and their caregiver(s), if applicable, will receive a glucometer and training on how to perform SMBG. Participants will be asked to monitor fasting blood glucose (FBG) 4 times a week. Participants will also be asked to monitor two 7-point SMBG profiles done on 2 nonconsecutive days in the 2-week period prior to Visit 3 (randomization), Visit 9 (Week 24), Visit 11 (Week 40).

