6.9.1.1. Rescue Therapy

If a participant develops severe, persistent hyperglycemia after randomization, a new antihyperglycemic medication (“rescue therapy”) may be medically indicated after investigator assessment.

Investigators will be trained on the application of criteria for deciding when and how to intervene with participants who do not reach glycemic targets. If met the following prespecified severe, persistent hyperglycemia criteria and no intercurrent cause of the hyperglycemia could be identified (investigators should first confirm that the participant is fully compliant with the assigned therapeutic regimen and that he or she does not have an acute condition causing severe hyperglycemia), rescue medication will be prescribed as an add-on to randomized treatment. Participants will continue in the trial until they complete all study visits.

Severe, Persistent Hyperglycemia

- If any of the FBG values within 1 week for 2 consecutive weeks,
 - $>270 \text{ mg/dL} (>15.0 \text{ mmol/L})$ from baseline to end of Week 5, or
 - $>240 \text{ mg/dL} (>13.3 \text{ mmol/L})$ from Week 6 to end of Week 11, or
 - $>200 \text{ mg/dL} (>11.1 \text{ mmol/L})$ from Week 12 to end of trial, or
 - $\text{HbA1c} \geq 8.5\% (\geq 69 \text{ mmol/mol})$ by and after Week 24

The date and time of rescue medication administration as well as the name and dosage regimen of the rescue medication must be recorded.

7. Discontinuation of Study Intervention and Participant Discontinuation/Withdrawal

Discontinuation of specific sites or of the study as a whole are handled as part of Section 10.1 Appendix 1.

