4.11. Safety Analyses

Unless specified otherwise, safety assessments will be based on the SS (see Section 3). All events that occur between the date of first dose of study drug to the date of patient's safety follow-up visit or patient's end of study participation will be included. Selected safety analyses may be conducted after excluding data after the introduction of another antihyperglycemic therapy. For rare events (<10 patients have the events), summary tables may not be generated, and individual patient level data will be listed.

Unless specified otherwise, comparisons of tirzepatide doses to placebo will be performed. For selected continuous safety parameters, difference among treatment mean change from baseline at scheduled visits will be assessed via a MMRM using REML. The model will include baseline HbA1c ($\leq 8.5\%$, $> 8.5\%$ [≤ 69 , > 69 mmol/mol]), any past prior use (yes or no) of any antihyperglycemic medication, treatment group, visit, treatment-by-visit interaction, baseline

value of the safety parameter and baseline of the safety parameter-by-visit interaction. To model the covariance structure within patients, the unstructured covariance matrix will be used. If this model fails to converge, the covariance structures specified in Section 4.8.3 will be tested in order.

For selected safety parameters, time-to-first-event analysis via cox-proportional hazards model may be conducted. For patients experiencing an event, “time-to-first-event” will be the time to the first occurrence of the event. For patients without the event, “time-to-event” will be censored at end of study participation (study discontinuation, safety follow-up visit, or date of death).

Where specified, rate of events will be analyzed using a generalized linear mixed-effects model assuming the number of events follow a negative binomial distribution, and with treatment as a fixed effect. The logarithm of years in specified time interval will be adjusted as an offset to account for possible unequal treatment duration in specified time interval between patients.

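### The Cox model for time to rescue (SAP 4.11.4.2) names no randomisation factor; stratifying it by the HbA1c category is a small, free improvement

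*SAP*

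**What the plan says.** Protocol Section 3 and SAP 1.1 list "Time to initiation of rescue therapy for severe persistent hyperglycemia" among the safety endpoints, outside type 1 error control. SAP 4.11.4.2 sets the analysis: given at least 10 episodes, "time-to-first-event analyses for the initiation of rescue therapy will be conducted by treatment using a cox proportional regression model". The general safety text in SAP 4.11 adds only that, for selected parameters, "time-to-first-event analysis via cox-proportional hazards model may be conducted". The general Cox statements in Protocol 9.3.1 and SAP 4.1 name no covariates or strata either.

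Other safety models are more explicit. In SAP 4.11.4.1, "The incidence of hypoglycemic event will be analyzed using logistic regression with treatment and stratification factors as fixed effects". The pancreatic-enzyme MMRM in SAP 4.11.4.3.1 also includes the stratification factors. The safety MMRMs in SAP 4.11 and 4.11.6.1 include the HbA1c category at 8.5% and prior antihyperglycemic use.

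On design, Protocol 4.1 states "Participants will be stratified based on HbA1c", split at 8.5%, and also by prior antihyperglycemic use. Protocol 6.9.1.1 defines the rescue criteria. One set is fasting glucose above 270, 240 or 200 mg/dL depending on study period ("If any of the FBG values within 1 week for 2 consecutive weeks"). The other is HbA1c of at least 8.5%, which applies only "by and after Week 24".

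**The concern.** Programmed literally, the rescue model contains treatment and nothing else. Yet the documents themselves suggest that baseline HbA1c predicts rescue. Entry HbA1c runs from 7.0% to 9.5%. A participant who enters above 8.5% already exceeds the later HbA1c criterion and meets it by not improving; one who enters at 7.0% must rise by 8.5 − 7.0 = 1.5 points. The fasting-glucose criteria measure a related aspect of glycemia.

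Leaving out a prognostic factor changes what a Cox model estimates: the treatment-only hazard ratio is closer to 1 than the hazard ratio within HbA1c strata, even with perfectly balanced arms. Some sensitivity is lost as well. At stake is how well the reported hazard ratio and interval describe the rescue contrast in a trial with 50 per arm and probably few rescue events.

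**Working it through.** **No plan figure to reproduce.** The documents give no hazard ratio, event count or power for time to rescue, and the assumed rates of rescue or treatment discontinuation in SAP Section 5 are redacted.

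**Inputs from the documents.** 50 participants per arm (SAP 5); HbA1c split at 8.5% (Protocol 4.1); default two-sided 0.05 (SAP 4.1), used here only as a yardstick for sensitivity.

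**Assumptions, not in the documents.** Placebo rescue 15% or 30%; true within-stratum treatment HR 0.3 or 0.5; 30% of participants above 8.5%; hazard in that stratum 2, 4 or 8 times the other; 10% dropout.

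**Model.** With the treatment period scaled to 1, the rescue hazard is h0 × (stratum HR)^s × (treatment HR)^a, where s = 1 above 8.5% and a = 1 on tirzepatide. h0 solves 1 − [0.7·exp(−h0) + 0.3·exp(−h0 × stratum HR)] = placebo rescue proportion. One dose is compared with placebo, with equal stratum shares in both arms. Hazard ratios come from 100,000 per arm. Rejection rates come from 3,000 trials of 50 versus 50, using the score (log-rank) test, so each has a standard error of at most √(0.25/3000) = 0.9 points.

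| Placebo rescue | True HR | Stratum HR | HR, treatment only | HR, stratified | Rejection, treatment only | Rejection, stratified | Gain (points) |
|---|---|---|---|---|---|---|---|
| 15% | 0.3 | 2 | 0.303 | 0.301 | 38.5% | 38.9% | 0.4 |
| 15% | 0.3 | 4 | 0.310 | 0.300 | 37.3% | 39.2% | 1.9 |
| 15% | 0.3 | 8 | 0.322 | 0.302 | 36.0% | 40.4% | 4.4 |
| 15% | 0.5 | 2 | 0.512 | 0.510 | 18.3% | 18.5% | 0.2 |
| 15% | 0.5 | 4 | 0.518 | 0.508 | 17.6% | 19.5% | 1.9 |
| 15% | 0.5 | 8 | 0.525 | 0.502 | 15.6% | 19.7% | 4.1 |
| 30% | 0.3 | 2 | 0.305 | 0.301 | 69.9% | 70.8% | 0.9 |
| 30% | 0.3 | 4 | 0.323 | 0.302 | 66.1% | 70.5% | 4.4 |
| 30% | 0.3 | 8 | 0.355 | 0.306 | 63.2% | 73.4% | 10.2 |
| 30% | 0.5 | 2 | 0.500 | 0.495 | 34.7% | 35.9% | 1.2 |
| 30% | 0.5 | 4 | 0.523 | 0.501 | 30.6% | 35.6% | 5.0 |
| 30% | 0.5 | 8 | 0.563 | 0.509 | 25.3% | 38.2% | 12.9 |

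The treatment-only HR is nearer 1 in every row.

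**The shift set against precision.** Take SE(log HR) as roughly 2/√events. For placebo rescue 30%, true HR 0.3 and stratum HR 4 (19.4 events on average), the shift is ln(0.323/0.302) = 0.067 and the SE is 2/√19.4 = 0.45, so the shift is about 0.15 SE. The largest shift in the table is ln(0.355/0.306) = 0.149, with SE 2/√19.9 = 0.45, or about 0.33 SE.

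**HbA1c as a continuous predictor.** A second two-arm simulation assumed baseline HbA1c with mean 8.0 and SD 0.75 limited to 7.0–9.5%, placebo rescue of 21–26% and true HR 0.40 (1,200 trials per scenario, Monte Carlo error about 1.4 points). Rejection rates:

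| Hazard per HbA1c point | Treatment only | Stratified at 8.5% | Adjusted for continuous HbA1c |
|---|---|---|---|
| ×2 | 35% | 36% | 36% |
| ×3 | 35% | 38% | 42% |
| ×4 | 39% | 43% | 46% |

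In the ×3 case the median treatment-only HR was 0.42 against a true 0.40.

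**Near the 10-episode threshold.** A four-arm check with 50 per arm, about 15 to 37 events in total and true HR 0.40 found no harm from stratifying or adjusting for HbA1c. Gains were about 0–2 points if the hazard doubles per HbA1c point, and about 2–9 points if it triples or quadruples.

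**The case against.** The strongest reply is that the SAP never chooses a treatment-only model. It uses the words by treatment for tables and summaries throughout, and here it simply does not mention covariates. A reader might infer that the randomisation factors have been deliberately excluded; the documents do not say so. That objection stands. The text is under-specified, and the safety models do not follow one rule: the general event-rate model in SAP 4.11 names treatment as its only fixed effect. But no general Cox statement supplies an adjustment by default, so a programmer following the text would fit treatment alone.

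A second reply is that sensitivity hardly matters here. SAP 4.11 says that neither p-values nor confidence intervals are used for hypothesis testing in safety interpretation. This also stands, and it limits the benefit mainly to the estimate and its interval.

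Third, the shift in the hazard ratio is small and reflects two different quantities, marginal and within-stratum, rather than an error. That is fair. The plan does not say which it wants.

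Fourth, a lean model is prudent if the Cox analysis can run on 10 episodes. If those are counted over four arms, three treatment terms plus HbA1c plus prior use would be five parameters for 10 events. This tells against a heavily adjusted model, but not against stratification, which adds none.

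**Conclusion.** The point holds as a minor improvement. SAP 4.11.4.2 leaves the randomisation factors unmentioned for this endpoint, and stratifying by the HbA1c category is a better pre-specified method than the model the text produces as written. The direction is clear if baseline HbA1c is prognostic, which the rescue criteria make likely. The size is nil to modest: about 0 to 5 points of rejection rate for a stratum HR of 2 to 4, and 4 to 13 points for a stratum HR of 8. All of this depends on assumed rescue rates, stratum share, treatment effect and prognostic strength.

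A reader might go further and infer a materially biased hazard ratio, or a loss of power that puts a conclusion at risk. The documents support neither. The shift is a fraction of a standard error in every scenario, no formal decision rests on this endpoint, the HbA1c criterion does not operate before Week 24, and no figure in the documents shows how strongly baseline HbA1c predicts rescue.

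**What to change.** In SAP 4.11.4.2, state that the Cox model has treatment as its only regression term and is stratified by the HbA1c randomisation category (≤8.5% or >8.5%). This adds no regression parameters, so it suits the 10-episode threshold. It also matches the design and brings this model closer to its neighbours. Fix the specification in advance and do not let it vary with the number of events beyond that threshold. SAP 4.1 allows additional analyses after database lock without changing the SAP, so naming the model now also avoids a later choice between adjusted and unadjusted results. The cost is one sentence in the SAP, with no new data and no effect on conduct. Label: free improvement, low severity.

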4.11.4.3. Pancreatitis

If data warrants, summaries of adjudicated and investigator-reported pancreatic events will be provided by treatment. Determination of investigator-reported events will be through the predefined SMQ search for acute pancreatitis and MedDRA PT of pancreatitis chronic. Detailed searching criteria can be found in Section 6.1, Appendix 1. Treatment-emergent adjudication-confirmed pancreatitis will be considered as AESI.

4.11.4.3.1. Pancreatic Enzyme Assessment

Observed pancreatic enzyme data (p-amylase and lipase) will be summarized by treatment and nominal visit. The number and proportion of patients with maximum postbaseline pancreatic enzyme values exceeding the following thresholds will be provided by maximum baseline pancreatic enzyme value ($\leq 1 \times$ upper limit of normal [ULN], $>1 \times$ ULN), and treatment: $\leq 1 \times$ ULN, (>1 to ≤ 3) \times ULN, (>3 to ≤ 5) \times ULN, (>5 to ≤ 10) \times ULN, $>10 \times$ ULN.

An MMRM analysis will be used to analyze each pancreatic enzyme with a log transformed (postbaseline measure/baseline measure) response variable and stratification factors, treatment, nominal visit, and treatment-by-nominal visit interaction as fixed effects, and baseline value as a covariate.

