- have been treated with insulin 1 year preceding Visit 1 and between Visit 1 and Visit 3; or have been treated with any antihyperglycemic medication 90 days preceding Visit 1 and between Visit 1 and Visit 3

Note: An exception is for the use of insulin for gestational diabetes or short-term use (≤ 14 days) for certain clinical situations such as acute illness, hospitalization, or elective surgery

- have history of chronic or acute pancreatitis prior to Visit 1
- be currently requiring or receiving treatment for diabetic retinopathy and/or macular edema
- have been treated with prescription drugs or similar other body weight loss medications including over-the-counter (OTC) medications that promote weight loss within 90 days prior to Visit 1 and/or between Visit 1 and Visit 3
- have been receiving chronic (>2 weeks or 14 days) systemic glucocorticoid therapy (excluding topical, intraocular, intranasal, or inhaled preparations) or had received such therapy within 30 days of Visit 1 or between Visits 1 and 3.

Number of Participants:

[figure not shown]
Approximately 200 participants (50 participants per arm) will be randomized in a **CCI** ratio (tirzepatide 5 mg once weekly [QW], tirzepatide 10 mg QW, tirzepatide 15 mg QW, and placebo QW).

Ethical Considerations of Benefit/Risk:

Considering the data that are available to date from previous clinical studies, and the measures taken to ensure the safety of the participants in this study, the potential risks related with tirzepatide are justified by the anticipated benefits a participant with T2DM may experience in the study.

Data Monitoring Committee: No

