- ^g Weight measurements must be in kilograms.
- ^h A dilated fundoscopic examination will be performed by an ophthalmologist or optometrist for all participants between Visit 2 and Visit 3 to confirm eligibility. A previous examination \leq 90 days meeting study requirements from Visit 1 is acceptable to confirm eligibility.
- ⁱ Includes counseling on diet and exercise, symptoms and management of hypoglycemia and hyperglycemia, etc.
- ^j All training should be repeated as needed to ensure participant compliance.
- ^k Participant is required to collect two 7-point SMBGs on nonconsecutive days prior to the next visit. A 7-point SMBG consists of measurements before and 2 hours after each of 3 main meals within the same day and at bedtime. These SMBG profiles will be collected by the participant within 2 weeks prior to the assigned visits. If more than 2 SMBG profiles are available, the 2 most recent nonconsecutive profiles should be used.
- ^l Participants should administer their first dose of study intervention at the end of this visit, after other study procedures and randomization.
- ^m A serum pregnancy test will be performed at Visit 1 for women of childbearing potential only.
- ⁿ A local urine pregnancy test must be performed at Visit 3 with the result available prior to randomization and first injection of study intervention(s) for women of childbearing potential only. Additional pregnancy tests will be performed at Visits 6, 9, and 11. Pregnancy tests may be performed at the investigator's discretion during the study. If required per local regulations and/or institutional guidelines, pregnancy testing can also occur at other times during the study treatment period. For sites who can't perform urine pregnancy test, a local serum pregnancy test can be performed instead.
- ^o Performed as needed to confirm postmenopausal status, see Section 10.4.
- ^p Screening visit assessment will serve as baseline.
- ^q The CKD-EPI equation will be used by the central lab to estimate and report eGFR.
- ^r Confirmation by hepatitis C virus RNA will be performed if positive for hepatitis C virus antibody.
- ^s Confirmation by hepatitis B virus DNA will be performed if positive for hepatitis B core antibody.
- ^t All PROs should be completed before any other study procedures if the participant is not adversely affected by the fasting condition or completed after the participant has sufficiently recovered from the preceding visit procedures.

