For safety interpretation, p-values will not be used for hypothesis testing. P-values will be considered as a number between 0 and 1 that gives an idea of how strong the evidence is for an imbalance between study intervention arms. The evidence for an imbalance is stronger toward 0 and weaker toward 1. Similarly, confidence intervals will not be used for hypothesis testing. They reflect the uncertainty of an estimate.

The definition of baseline and postbaseline are provided in [Table GPIU.4.1](#).

Table GPIU.4.1. Baseline and Postbaseline Definition for Safety Analysis

Analysis Set	Analysis Type	Baseline	Postbaseline
SS	1.1) Treatment-Emergent Adverse Events	The baseline period is defined as the start of screening and ends prior to the first dose of study treatment (typically at Week 0). If the first dose date is missing then the randomization date will be used instead of first dose date.	Starts at or after the first dose of study treatment and ends at the end of the study period (including off-drug follow up visit).
SS	1.2) Treatment-Emergent Abnormal Labs and Vital Signs.	For labs, baseline period is defined as prior to the first dose time and will include all scheduled and unscheduled measurements. If the first dose time is missing then any data collected on the date of the first dose will be treated as baseline. For vital signs, baseline period is defined as measurements collected prior to the first dose. If the first dose date is missing then the randomization date will be used instead of first dose date.	Postbaseline will be defined as after the baseline period through the end of the study participation. All scheduled and unscheduled measurements will be included.
SS	1.3) Change from Baseline for Labs, and Vital Signs.	The last scheduled and unscheduled non-missing assessment recorded during the baseline period defined above (1.2).	Postbaseline will be defined as above (1.2). Only scheduled visits will be included.

Abbreviations: ED = early discontinuation; SS = Safety Analysis Set.

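### The pancreatic enzyme MMRM takes the log of the response but, read literally, not of the baseline covariate; specifying log(baseline) is a small, free improvement

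*SAP*

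**What the plan says.** SAP 4.11.4.3.1 defines the model for each enzyme: "An MMRM analysis will be used to analyze each pancreatic enzyme with a log transformed (postbaseline measure/baseline measure) response variable". The terms are the stratification factors, treatment, nominal visit, "and treatment-by-nominal visit interaction as fixed effects, and baseline value as a covariate". The log is attached to the response only, and no scale is given for the covariate.

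The general safety MMRM in SAP 4.11 does not settle the matter. Its terms end with the baseline "value of the safety parameter and baseline of the safety parameter-by-visit interaction", again with no scale. The vital-sign model in SAP 4.11.6.1 and the laboratory model in Protocol 9.3.6.4 are equally silent, but their responses are plain changes from baseline, so the question does not arise there.

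Other relevant statements:

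- SAP 4.11: "For safety interpretation, p-values will not be used for hypothesis testing". Confidence intervals are treated the same way and are there to show uncertainty.
- Protocol 1.1: "Approximately 200 participants (50 participants per arm) will be randomized".
- Protocol 1.3, in the footnote attached to pancreatic amylase and lipase: "Screening visit assessment will serve as baseline".
- SAP 4.11.4.3.1 also plans a table: "The number and proportion of patients with maximum postbaseline pancreatic enzyme values exceeding the following thresholds will be provided by maximum baseline pancreatic enzyme value". It splits baseline at 1 × ULN and does not use the MMRM covariate.

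**The concern.** Modelling log(postbaseline/baseline) treats enzyme changes as multiplicative. That response equals log(postbaseline) minus log(baseline), so regression to the mean makes it depend on log(baseline). Entering the raw value fits a straight line to a relation that is curved on that scale. If enzyme values are right-skewed, the few highest baselines also get the most pull on the slope. High baselines can occur: Protocol 5.2 excludes a history of pancreatitis but sets no amylase or lipase limit, and the SAP provides for baseline values above 1 × ULN.

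What is at stake is precision in the dose-placebo enzyme ratios. With about 50 participants per arm, pancreatitis events may be too few to summarize, and this is the only model-based comparison of the enzymes that the readable text describes.

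**Working it through.** **No plan figure to reproduce.** The documents give no SD, correlation, effect size or precision for this analysis. The only design input is 4 × 50 = 200 participants. Everything below rests on assumed values.

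**Assumed model.** Log baseline X has SD s. Log postbaseline Y has the same SD, and its correlation with X is ρ. Write Y = ρX + e (plus treatment effect), with Var(e) = s²(1 − ρ²). The response is then D = Y − X = −(1 − ρ)X + e.

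1. *Log covariate.* X is fully adjusted for, so the residual variance is s²(1 − ρ²).
2. *Raw covariate exp(X).* The squared correlation between X and exp(X) is r² = s²/(exp(s²) − 1). A part of X with variance s²(1 − r²) is left over, so the residual variance is s²(1 − ρ²) + (1 − ρ)²s²(1 − r²).
3. *Ratio, raw to log.* 1 + (1 − ρ)(1 − r²)/(1 + ρ). The SE ratio is its square root.

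Worked example with s = 0.8 and ρ = 0.5: r² = 0.64/(exp(0.64) − 1) = 0.714. The variance ratio is 1 + (0.5 × 0.286)/1.5 = 1.095, and the SE ratio is √1.095 = 1.047.

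| s | r² | Variance ratio, ρ = 0.5 | Variance ratio, ρ = 0.7 | SE ratio, ρ = 0.5 | SE ratio, ρ = 0.7 |
|---|---|---|---|---|---|
| 0.4 | 0.922 | 1.026 | 1.014 | 1.013 | 1.007 |
| 0.5 | 0.880 | 1.040 | 1.021 | 1.020 | 1.011 |
| 0.6 | 0.831 | 1.056 | 1.030 | 1.028 | 1.015 |
| 0.8 | 0.714 | 1.095 | 1.050 | 1.047 | 1.025 |

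Outside this range the SE ratio runs from 1.004 (s = 0.3, ρ = 0.7) to 1.107 (s = 1.0, ρ = 0.3, the most extreme case computed).

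**Simulation check.** Four arms of 50, one postbaseline visit, complete data, a true ratio of 1.3 for each dose (log 1.3 = 0.262), and 3000 runs per scenario. The fitted terms were arm and one baseline covariate, so average leverage is 5/200 = 0.025. Rows with ρ = 0.5:

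| s | Empirical SE: raw | log | unadjusted | Mean maximum leverage: raw | log |
|---|---|---|---|---|---|
| 0.4 | 0.070 | 0.069 | 0.080 | 0.117 | 0.065 |
| 0.5 | 0.088 | 0.086 | 0.099 | 0.141 | 0.065 |
| 0.8 | 0.142 | 0.138 | 0.158 | 0.220 | 0.065 |

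- *Leverage.* The raw-to-log ratio of maximum leverage is 0.141/0.065 = 2.2 at s = 0.5 and 0.220/0.065 = 3.4 at s = 0.8.
- *Bias.* Mean estimates lay between 0.260 and 0.264 in every scenario, with either covariate.
- *Gain retained.* At s = 0.5 and ρ = 0.5, adjusting for raw baseline cuts the SE from 0.099 to 0.088; log baseline takes it to 0.086.

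**The case against.** The strongest reply is that the SAP never says the covariate is untransformed. It uses the same generic wording for baseline in its other safety models, so this may be stock phrasing, with log(baseline) intended. That stands: the raw scale is the literal reading, not a declared choice. It does not remove the need for an edit, because a programmer following the text would enter the raw value.

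The second reply is that the effect is small and its size assumed. That also stands. Residual variance makes it look larger than it is: on the SE scale the 1.4% to 9.5% becomes 0.7% to 4.7%, and a raw covariate keeps most of the benefit of adjustment.

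The third is that little depends on this model. The listed pancreatic safety endpoint is adjudicated events (Protocol 3), and Protocol 8.3.4.3 itself gives serial enzyme measurement limited predictive value in people without symptoms. No decision rule or type 1 error control is attached. This sets the priority, but since the intervals are meant to convey uncertainty, their width still has some value.

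A reader might go further and infer that a few high baselines would dominate the adjustment, or that the dose-placebo ratios would be distorted. Neither is supported. Leverage does rise, but it acts on the slope of a covariate that randomization balances in expectation, and the simulation showed no bias.

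**Conclusion.** The point holds as a low-priority clarification. On its literal reading, the enzyme MMRM pairs a log-ratio response with a raw baseline covariate. Under a lognormal model with log-scale SD 0.4 to 0.8 and correlation 0.5 to 0.7, this costs about 1.4% to 9.5% in residual variance. In terms of information that is roughly 3 to 17 of 200 participants: 200 × (1 − 1/1.014) ≈ 3 and 200 × (1 − 1/1.095) ≈ 17. Maximum leverage is roughly two to three times as high at SD 0.5 to 0.8.

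The SD, the correlation and the lognormal shape are assumptions; the documents give none of them. The simulation covered one visit with complete data and no stratification terms, so it does not test the full MMRM with missing visits. Nothing here suggests that the planned comparison is invalid or that a pancreatic safety conclusion would change.

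**What to change.** In SAP 4.11.4.3.1, insert *log-transformed* before the baseline value in the list of model terms, so that covariate and response are on the same scale. If the sponsor already intends log(baseline), the same edit records it.

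The cost is one word in the SAP and one line of code. It needs no new data and no change to the design, and it leaves the threshold tables as they are. With log(baseline) in the model, the treatment contrast is also the same whether the response is written as log(postbaseline) or as the log ratio, which makes the result simpler to report.
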